Appendix 1. Table Shells

1. Study variables (Section 25a)

Variable name	Variable description	Variable type	Variable coding/values
id	Unique ID. Each participant possesses a unique ID that indicates the community (1 st digit), family code (2 nd -4 th digit), and the participant type (5 th digit: female caregiver '1', male caregiver '2', or child '3').	Nominal	11111-99999
int_location	Community (numeric identifier) of residence	Nominal	1: Tbek 2: Ghoi 3: Sukzero/Taragok 4: Malou/Anglican Church/Lenguet 5: Pariak
household	Household (numeric identifier).	Nominal	1-9999
id_fv	Caregiver ID (numeric identifier)	Nominal	1-9999
Id_ch	Child ID (numeric identifier)	Nominal	1-9999
allocation	Study condition (BeThere vs. waitlist) Note: the labelling will not be revealed until after primary analyses have been completed	Nominal	0: TBC 1: TBC
betheregrp	BeThere group number Note: if waitlist groups are not enumerated then do not include this variable in the dataset until primary analyses have been completed	Nominal	1-99
assessment	Assessment number Note: do not include midline data until the primary analyses have been completed	Ordinal	0: Baseline 1: Midline 2: Endline 3: Follow up
assessweeks	Number of weeks since enrolment	Continuous	Time since baseline (in weeks)
assessdate	Date of the assessment	Date	DD-Mon-YY
cg_gender	Gender (caregiver)	Nominal	1: Female 2: Male
num_caregivers	Number of caregivers in the household	Continuous	1-2
ic_age_t1	Child age (in years; caregiver-reported)	Continuous	3-14
parenting	Total score on parenting measure (caregiver reported)	Numeric, continuous	24-120
parenting_01, parenting_02, parenting_03, parenting_04, parenting_05 (reverse), parenting_06, parenting_07,	Item score on parenting measure (caregiver-reported)	Numeric, continuous	1-5

parenting_08, parenting_09, parenting_10, parenting_11, parenting_12, parenting_13, parenting_14, parenting_15 (reverse), parenting_16, parenting_17 (reverse), parenting_18 (reverse), parenting_19 (reverse), parenting_20 (reverse), parenting_21, parenting_22, parenting_23, parenting_24			
parenting_warmth_cg	Total score on parenting warmth subscale (caregiver reported)	Numeric, continuous	17-85
parenting_01, parenting_02, parenting_03, parenting_04, parenting_06, parenting_07, parenting_08, parenting_09, parenting_10, parenting_11, parenting_12, parenting_13, parenting_14, parenting_16, parenting_21, parenting_22, parenting_23	Item score on parenting warmth subscale (caregiver reported)	Numeric, continuous	1-5
parentingharsh_cg	Total score on harsh parenting subscale (caregiver reported)	Numeric, continuous	6-30
parenting_05, parenting_15, parenting_17, parenting_18, parenting_19, parenting_20	Item score on harsh parenting subscale (caregiver reported)	Numeric, continuous	1-5
parenting_ic	Total score on parenting measure (child reported)	Numeric, continuous	24-120
parenting_01_ic, parenting_02_ic, parenting_03_ic,	Item score on parenting measure (child-reported)	Numeric, continuous	1-5

parenting_04_ic, parenting_05_ic (reverse), parenting_06_ic, parenting_07_ic, parenting_08_ic, parenting_09_ic, parenting_10_ic, parenting_11_ic, parenting_12_ic, parenting_13_ic, parenting_14_ic, parenting_15_ic (reverse), parenting_16_ic, parenting_17_ic (reverse), parenting_18_ic (reverse), parenting_19_ic (reverse), parenting_20_ic (reverse), parenting_21_ic, parenting_22_ic, parenting_23_ic, parenting_24_ic			
parenting_warmth_ic	Total score on parenting warmth subscale (child reported)	Numeric, continuous	17-85
parenting_01_ic, parenting_02_ic, parenting_03_ic, parenting_04_ic, parenting_06_ic, parenting_07_ic, parenting_08_ic, parenting_09_ic, parenting_10_ic, parenting_11_ic, parenting_12_ic, parenting_13_ic, parenting_14_ic, parenting_16_ic, parenting_21_ic, parenting_22_ic, parenting_23_ic	Item score on parenting warmth subscale (caregiver reported)	Numeric, continuous	1-5
parentingharsh_ic	Total score on harsh parenting subscale (child reported)	Numeric, continuous	6-30
parenting_05_ic, parenting_15_ic, parenting_17_ic, parenting_18_ic, parenting_19_ic, parenting_20_ic	Item score on harsh parenting subscale (child reported)		1-5
k	Total score on Kessler-10 (caregiver-	Numeric,	10-50

	reported)	continuous	
k_01 – k_10	Item score on Kessler-10 (caregiver-reported)	Numeric, continuous	1-5
stress	Total score on stress scale (caregiver-reported)	Numeric, continuous	18-90
stress_01 – stress_18 (stress_04, stress_15, and stress_18 reverse scored)	Item score on stress scale (caregiver-reported)	Numeric, continuous	1-5
wembws	Total score on Warwick-Edinburgh Mental Wellbeing Scale (caregiver-reported)	Numeric, continuous	14-70
wembws_01 – wembws_14	Item score on Warwick-Edinburgh Mental Wellbeing Scale (caregiver-reported)	Numeric, continuous	1-5
kkd	Total score on Kid_KINDL (caregiver-reported)	Numeric, continuous	25-125
kkd_01 – kkd_25 (kkd_02, kkd_03, kkd_04, kkd_06, kkd_07, kkd_08, kkd_16, kkd_17, kkd_21, and kkd_23 reverse scored)	Item score on Kid_KINDL (caregiver-reported)	Numeric, continuous	1-5
kkd_phys_wb	Total score on Kid_KINDL Physical Wellbeing subscale (caregiver-reported)	Numeric, continuous	4-20
kkd_01 – kkd_04 (kkd_02, kkd_03, and kkd_04 reverse scored)	Item score on Kid_KINDL Physical Wellbeing subscale (caregiver-reported)	Numeric, continuous	1-5
kkd_emot_wb	Total score on Kid_KINDL Emotional Wellbeing subscale (caregiver-reported)	Numeric, continuous	4-20
kkd_05 – kkd_08 (kkd_06, kkd_07, and kkd_08 reverse scored)	Item score on Kid_KINDL Emotional Wellbeing subscale (caregiver-reported)	Numeric, continuous	1-5
kkd_self_esteem	Total score on Kid_KINDL Self-esteem subscale (caregiver-reported)	Numeric, continuous	4-20
kkd_09 – kkd_12	Item score on Kid_KINDL Self-esteem subscale (caregiver-reported)	Numeric, continuous	1-5
kkd_family	Total score on Kid_KINDL Family subscale (caregiver-reported)	Numeric, continuous	5-25
kkd_13 – kkd_17 (kkd_16 and kkd_17, kkd_21 reverse scored)	Item score on Kid_KINDL Family subscale (caregiver-reported)	Numeric, continuous	1-5
kkd_soc_contacts	Total score on Kid_KINDL Social Contacts subscale (caregiver-reported)	Numeric, continuous	4-20
kkd_18 – kkd_21 (kkd_21 reverse scored)	Item score on Kid_KINDL Social Contacts subscale (caregiver-reported)	Numeric, continuous	1-5
kkd_add_qs	Total score on Kid_KINDL Additional Questions subscale (caregiver-reported)	Numeric, continuous	4-20

kkd_22 – kkd_25 (kkd_23 reverse scored)	Item score on Kid_KINDL Additional Questions subscale (caregiver-reported)	Numeric, continuous	1-5
Kkdchild714	Total score on Kid_KINDL (child-reported)	Numeric, continuous	25-125
kkdchild714_01 – kkdchild714_25 (kkdchild714_01, kkdchild714_02, kkdchild714_03, kkdchild714_06, kkdchild714_07, kkdchild714_08, kkdchild714_15, kkdchild714_16, kkdchild714_21, and kkdchild714_23 reverse scored)	Item score on Kid_KINDL (child-reported)	Numeric, continuous	1-5
kkdchild714_phys_wb	Total score on Kid_KINDL Physical Wellbeing subscale (child -reported)	Numeric, continuous	4-20
kkdchild714_01 – kkdchild714_04 (kkdchild714_01, kkdchild714_02, and kkdchild714_03 reverse scored)	Item score on Kid_KINDL Physical Wellbeing subscale (child -reported)	Numeric, continuous	1-5
kkdchild714_emot_wb	Total score on Kid_KINDL Emotional Wellbeing subscale (child -reported)	Numeric, continuous	4-20
kkdchild714_05 – kkdchild714_08 (kkdchild714_06, kkdchild714_07, and kkdchild714_08 reverse scored)	Item score on Kid_KINDL Emotional Wellbeing subscale (child -reported)	Numeric, continuous	1-5
kkdchild714_self_esteem	Total score on Kid_KINDL Self-esteem subscale (child -reported)	Numeric, continuous	4-20
kkdchild714_09 – kkdchild714_12	Item score on Kid_KINDL Self-esteem subscale (child -reported)	Numeric, continuous	1-5
kkdchild714_family	Total score on Kid_KINDL Family subscale (child -reported)	Numeric, continuous	5-25
kkdchild714_13 – kkdchild714_17 (kkdchild714_15 and kkdchild714_16 reverse scored)	Item score on Kid_KINDL Family subscale (child -reported)	Numeric, continuous	1-5
kkdchild714_soc_contacts	Total score on Kid_KINDL Social Contacts subscale (child -reported)	Numeric, continuous	4-20
kkdchild714_18 –	Item score on Kid_KINDL Social	Numeric,	1-5

kkdchild714_21 (kkdchild714_21 reverse scored)	Contacts subscale (child -reported)	continuous	
kkdchild714_add_qs	Total score on Kid_KINDL Additional Questions subscale (child -reported)	Numeric, continuous	4-20
kkdchild714_22 – kkdchild714_25 (kkdchild714_23 reverse scored)	Item score on Kid_KINDL Additional Questions subscale (child -reported)	Numeric, continuous	1-5
gcs	Total score on Group Cohesiveness Scale (caregiver-reported)	Numeric, continuous	7-35
gcs_01, gcs_02, gcs_03, gcs_04, gcs_05, gcs_06, gcs_07 (reverse)	Item score on Group Cohesiveness Scale (caregiver-reported) Note: Item gcs_07 was reverse scored to improve internal consistency. Cognitive interviews further revealed that this item referred to a behaviour that reflected lack of group cohesion and respect in the study context, further supporting the decision to reverse score this item.	Numeric, continuous	1-5
moa	Total score on Mechanisms of Action scale (caregiver-reported)	Numeric, continuous	5-25
moa_01 –moa_05	Item score on Mechanisms of Action scale (caregiver-reported)	Numeric, continuous	1-5
attendance	Number of sessions attended	Numeric, continuous	0-9
competence	ENACT score (12 of 15 items) measured post-training/pre-implementation and during training; % scored harmful vs. not harmful	Proportion	0-100
fidelity	Total score on fidelity tool	Numeric, continuous	72-216

2. Characteristics of the sample at baseline (Section 25b)

	Overall sample (n=XX)	BeThere (n=XX)	Waitlist Control (n=XX)
Location, n (%)			
Tibek	n (%)	n (%)	n (%)
Ghoi	n (%)	n (%)	n (%)
Sukzero/Taragok	n (%)	n (%)	n (%)
Malou/Anglican Church/Lenguet	n (%)	n (%)	n (%)
Pariak	n (%)	n (%)	n (%)
Caregiver age, M (SD)	M (SD)	M (SD)	M (SD)
Caregiver gender, n (%)			
Female	n (%)	n (%)	n (%)
Male	n (%)	n (%)	n (%)
Caregiver nationality, n (%)			
South Sudanese	n (%)	n (%)	n (%)
Sudanese	n (%)	n (%)	n (%)
Ugandan	n (%)	n (%)	n (%)
Ethiopian	n (%)	n (%)	n (%)
Kenyan	n (%)	n (%)	n (%)
Other	n (%)	n (%)	n (%)
Caregiver marital status, n (%)			
Single	n (%)	n (%)	n (%)
Married	n (%)	n (%)	n (%)
Widowed	n (%)	n (%)	n (%)
Divorced	n (%)	n (%)	n (%)
Separated	n (%)	n (%)	n (%)
Other	n (%)	n (%)	n (%)
Caregiver education level, n (%)			
No schooling	n (%)	n (%)	n (%)
Primary school	n (%)	n (%)	n (%)
Secondary school	n (%)	n (%)	n (%)
Vocational training	n (%)	n (%)	n (%)
University/college	n (%)	n (%)	n (%)
Currently working (caregiver), n (%)	n (%)	n (%)	n (%)
Caregiver financial situations, n (%)			
In deep financial trouble	n (%)	n (%)	n (%)
In some financial trouble	n (%)	n (%)	n (%)
Somewhat financially secure	n (%)	n (%)	n (%)
Very financially secure	n (%)	n (%)	n (%)
Do not wish to disclose/no answer	n (%)	n (%)	n (%)
Type of house, n (%)			
Grass thatch house	n (%)	n (%)	n (%)
Plastic house	n (%)	n (%)	n (%)
Modern house	n (%)	n (%)	n (%)
Other	n (%)	n (%)	n (%)
Household size, M (SD)	M (SD)	M (SD)	M (SD)

Relationship to child, n (%)				
	Mother	n (%)	n (%)	n (%)
	Father	n (%)	n (%)	n (%)
	Grandmother	n (%)	n (%)	n (%)
	Grandfather	n (%)	n (%)	n (%)
	Other relative	n (%)	n (%)	n (%)
	Non-relative guardian	n (%)	n (%)	n (%)
Child age, M (SD)		M (SD)	M (SD)	M (SD)
Child gender, n (%)				
	Female	n (%)	n (%)	n (%)
	Male	n (%)	n (%)	n (%)

3. Table Shell for Outcome Models (Section 27a)

		BeThere	WLC	Difference in change from baseline to endline	Cohen's d
Primary Outcome					
Parenting (Caregiver-reported)					
	Baseline	M (SD)	M (SD)		
	Endline	M (SD)	M (SD)		
	Change from baseline to endline	B (95% CI)	B (95% CI)	B (95% CI)	d
Secondary Outcomes					
Parenting (Child-reported)					
	Baseline	M (SD)	M (SD)		
	Endline	M (SD)	M (SD)		
	Change from baseline to endline	B (95% CI)	B (95% CI)	B (95% CI)	d
Child wellbeing (Caregiver-reported)					
	Baseline	M (SD)	M (SD)		
	Endline	M (SD)	M (SD)		
	Change from baseline to endline	B (95% CI)	B (95% CI)	B (95% CI)	d
Child wellbeing (Child-reported)					
	Baseline	M (SD)	M (SD)		
	Endline	M (SD)	M (SD)		
	Change from baseline to endline	B (95% CI)	B (95% CI)	B (95% CI)	d
Caregiver psychological distress					
	Baseline	M (SD)	M (SD)		
	Endline	M (SD)	M (SD)		
	Change from baseline to endline	B (95% CI)	B (95% CI)	B (95% CI)	d
Caregiver stress					
	Baseline	M (SD)	M (SD)		
	Endline	M (SD)	M (SD)		
	Change from baseline to endline	B (95% CI)	B (95% CI)	B (95% CI)	d
Caregiver wellbeing					
	Baseline	M (SD)	M (SD)		
	Endline	M (SD)	M (SD)		
	Change from baseline to endline	B (95% CI)	B (95% CI)	B (95% CI)	d

4. Table Shell for Mediation Models (*Exposure: BeThere Intervention, Outcome: Child wellbeing*)

Path	Model 1: Parallel multiple mediation		Model 2: Serial multiple mediation	
	B (95% CI)	Indirect Effect	B (95% CI)	Indirect Effect
a ₁	BeThere → Caregiver Wellbeing (endline)		BeThere → Caregiver Wellbeing (midline)	
a ₂	BeThere → Caregiver Distress (endline)		BeThere → Caregiver Distress (midline)	
a ₃	BeThere → Caregiver Stress (endline)		BeThere → Caregiver Stress (midline)	
a ₄	BeThere → Caregiver Parenting (endline)		BeThere → Caregiver Parenting (endline)	
b ₁	Caregiver Wellbeing → Child Wellbeing		Caregiver Wellbeing → Child Wellbeing	
b ₂	Caregiver Distress → Child Wellbeing		Caregiver Distress → Child Wellbeing	
b ₃	Caregiver Stress → Child Wellbeing		Caregiver Stress → Child Wellbeing	
b ₄	Parenting → Child Wellbeing		Parenting → Child Wellbeing	
c'	BeThere → Child Wellbeing (Direct effect)		BeThere → Child Wellbeing (Direct effect)	
c	BeThere → Child Wellbeing (Total Effect)		BeThere → Child Wellbeing (Total Effect)	
d ₁	--		Caregiver wellbeing → Parenting	
d ₂	--		Caregiver Distress → Parenting	
d ₃	--		Caregiver Stress → Parenting

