14. Timing of final analysis

All analyses will be conducted after completion of data collection for the trial. The statistician and PI will be masked to study condition during data collection, cleaning, and the primary effectiveness analyses. Secondary analyses examining mediators that relate to intervention group characteristics (e.g., BeThere Mechanism of Action, Group Cohesion) or require analysis of intervention midline assessment data will be conducted after effectiveness analyses are finalized to preserve masking.

15. Timing of outcome assessments

Data used for this study will be collected by research assistants at baseline, midline (BeThere session 5), endline (within 2-3 weeks following session 9 or approximately 10-12 weeks post-enrollment), and follow-up (12 weeks after completion of the final session or approximately 22 weeks post-enrollment). The midline assessment was only administered to the experimental (i.e., BeThere) group and not to the waitlist control group.

SECTION 4: STATISTICAL PRINCIPLES

16. Level of statistical significance

A significance level of $\alpha=0.05$ will be applied.

17. Adjustments for multiplicity

We do not plan to adjust for multiple testing.

18. Confidence intervals

Results will be presented as coefficients and 95% CIs.

19. Adherence and protocol deviations

Participant adherence to the intervention will be measured using intervention session attendance records. Completion of the intervention will be defined as having attended seven or more sessions. We will report the mean (SD) and median (IQR) number of sessions attended in the BeThere group.

Facilitator fidelity to the intervention will be measured using a fidelity checklist. We will report the mean (SD) and median (IQR) scores on the fidelity checklist as an indicator of trial implementation quality.

Any major deviations from the protocol will be reported in the main outcomes paper.

20. Analysis populations

The primary analysis will be conducted on the intent-to-treat sample, meaning that all participants will be included and analyzed as randomized. No enrolled participants were excluded from the main analytic sample. We will also conduct a per protocol analysis including waitlist control participants who completed all assessments and did not participate in any BeThere intervention components and only BeThere intervention participants who completed seven or more intervention sessions and did not drop out of the study.

SECTION 5: TRIAL POPULATION

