- **Mechanisms of Action:** Total score on a 5-item measure developed to assess hypothesized mechanisms for the BeThere intervention (e.g., relaxation techniques, stress and anger management, positive parenting practices). Mechanisms of action were assessed at baseline, midline, endline, and follow up.
- **Caregiver psychological distress (see above)**
- **Caregiver stress (see above)**
- **Caregiver wellbeing (see above)**
- **Parenting (see above)**

Implementation variables

- **Attendance:** Number of sessions attended (participant-level; range: 0-9)
- **Facilitator competence:** ENACT score (12 of 15 items) measured post-training/pre-implementation and during training. We will operationalize facilitator competence as the % of harmful (item score=1) and % of not harmful (item score=3-4) behaviors observed
- **Intervention fidelity:** Total score on BeThere fidelity tool (8-items) assessing the number of intervention components adequately implemented per session (Range: 72-216)

Study outcome measures and timepoints

Measures	Baseline	Randomisation	Midline*	Endline	Follow up	Ongoing
Caregiver						
Parenting (BPS)	X			X	X	
Psychological Distress (K10)	X		X	X	X	
Caregiver stress	X		X	X	X	
Psychosocial wellbeing (WEMWBS)	X		X	X	X	
Child wellbeing (KINDL)	X			X	X	
Group cohesion (GCS)			X	X	X	
Mechanisms of action (MOA)	X		X	X	X	
Child						
Parenting (BPS – Child Version)	X			X	X	
Psychosocial wellbeing (KINDL)	X			X	X	
Randomisation		X				
Adverse events						X

*Midline assessments administered to BeThere study arm only

27a. Analysis methods

Data Management

We will prepare both a long and wide final dataset. The long dataset will include a separate observation for each assessment. The wide dataset will include one observation per individual with variables for each assessment period. The final dataset will include the following variables:

- Community identifier
- Household identifier
- Individual identifier (caregivers, child)
- Allocation [masked: will be coded 0 or 1 without a label until primary analyses are complete]
- BeThere group number/identifier
- Assessment number/time point
- Assessment date
- Caregiver age
- Child age
- Caregiver gender
- Number of caregivers in the household
- Caregiver-reported parenting items and total score
- Child-reported parenting items and total score
- Caregiver psychological distress items and total score
- Caregiver stress items and total score
- Caregiver wellbeing items and total score

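### The serial mediation model (Model 2) needs BeThere effects on midline mediators, but the waitlist arm has no midline data, so its serial indirect effects cannot be estimated

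*SAP*

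**What the plan says.** Appendix 1, item 4 of the SAP sets out two mediation models under the label "Exposure: BeThere Intervention, Outcome: Child wellbeing". Model 1 (parallel) places all four mediators at endline. Model 2 (serial) places the three caregiver mediators earlier: a1 is "BeThere → Caregiver Wellbeing (midline", a2 is "BeThere → Caregiver Distress (midline" and a3 is "BeThere → Caregiver Stress (midline", each marked as midline. Path a4 stays at endline, "BeThere → Caregiver Parenting (endline". Paths d1 to d3 then link the caregiver measures to parenting, beginning with "Caregiver wellbeing → Parenting".

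On data collection, Section 15 states: "The midline assessment was only administered to the experimental (i.e., BeThere) group and not to the waitlist control group". Section 26 repeats this, and the footnote to its schedule table says "Midline assessments administered to BeThere study arm only".

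Section 27a (Mediation Analyses) promises natural direct and indirect effects and the proportion mediated from a structural equation model with 500 bootstrap replications. Its text gives no time points for the mediators and does not mention the missing comparator.

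**The concern.** A treatment effect on a mediator needs that mediator in both arms. Model 2 asks for three such effects at a visit the waitlist arm never had.

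Mediation is primary objective 3 and the subject of one of the two planned papers. Model 2 is the only specified model with paths from caregiver mental health to parenting, which is the family-stress chain that motivates BeThere. As written, it will either fail to run or return numbers produced by an unstated assumption. Section 14 schedules analyses that need midline data after the effectiveness analyses are final, so the failure would come to light once allocation is known. A substitute could then be chosen with the results in view.

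**Working it through.** The plan states no figure to reproduce; the question is whether the model is identified.

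**Model.** Let T = 1 for BeThere and 0 for waitlist. Let M1 to M3 be midline wellbeing, distress and stress, P endline parenting, and Y child wellbeing. Model 2 is then:

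- Mk = ik + ak·T + error, for k = 1, 2, 3
- P = p0 + a4·T + d1·M1 + d2·M2 + d3·M3 + error
- Y = y0 + c'·T + b1·M1 + b2·M2 + b3·M3 + b4·P + error

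**Rows with midline data.** All are BeThere, so T is constant at 1. Section 11 gives 956 caregivers enrolled but no arm counts; 956 / 2 = 478 per arm is assumed here, and the ranks do not depend on it.

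| Regression | Columns | Rank |
|---|---|---|
| a1 to a3 (intercept, T) | 2 | 1 |
| a1 to a3 plus three baseline scores | 5 | 4 |
| Parenting on T and midline mediators (a4, d1 to d3) | 5 | 4 |
| Child wellbeing on T, midline mediators and parenting (c', b1 to b4) | 6 | 5 |

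Each is one short: the intercept and the treatment effect cannot be separated, and baseline adjustment does not change that.

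**All rows, full-information likelihood.** There are 25 parameters: 17 intercepts and paths (3 + 3 + 2 + 3 + 2 + 3 + 1), 6 residual variances and covariances of the mediators, and 2 residual variances for P and Y. The observable moments are the means and covariances of (M1, M2, M3, P, Y) in BeThere and of (P, Y) alone in waitlist. A numerical check of the Jacobian of these moments gives rank 22 of 25. With midline observed in both arms it gives 25 of 25.

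The three missing dimensions can be shown by hand. For any number δ and any k, replace:

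- ik by ik + δ, and ak by ak − δ
- p0 by p0 − dk·δ, and a4 by a4 + dk·δ
- y0 by y0 − bk·δ, and c' by c' + bk·δ

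Every observable mean and covariance stays the same. There is one free δ per midline mediator, and 25 − 3 = 22.

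**Illustration with arbitrary values** (M1 only, the other two mediators set aside). Take i1 = 0.10, a1 = 0.30, p0 = 0.05, a4 = 0.15, d1 = 0.20, y0 = 0.20, c' = 0.10, b1 = 0.10, b4 = 0.30, and shift by δ = 0.30:

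| Quantity | Before | After |
|---|---|---|
| a1 | 0.30 | 0.00 |
| a4 | 0.15 | 0.15 + 0.20 × 0.30 = 0.21 |
| c' | 0.10 | 0.10 + 0.10 × 0.30 = 0.13 |
| Serial a1 × d1 × b4 | 0.018 | 0.000 |
| a1 × b1 | 0.030 | 0.000 |
| a4 × b4 | 0.045 | 0.063 |
| Indirect effect (sum of the three rows above) | 0.093 | 0.063 |
| Total (c' + indirect) | 0.193 | 0.193 |
| Proportion mediated | 0.093 / 0.193 = 48% | 0.063 / 0.193 = 33% |

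Both columns fit the observable data equally well. The total effect is fixed; the serial effect and the proportion mediated are not. In general the indirect effect moves by −δ × bk, so it is identified only if b1 to b3 are zero.

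**Possible rescues in the plan.** Section 27a mentions imputing missing data where possible during cleaning. Section 28 covers prorating of missing items and says multiple imputation is not needed in the first-line models. Neither addresses a variable absent by design in a whole arm. Such a variable carries no information on that arm's mean, so imputation would only return its own assumption. Carrying baseline forward would assume no change on the waitlist. Section 14 and the variable list in Appendix 1, item 1 mention midline data only to protect masking.

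**The case against.** The strongest reply is about scope. Objective 3 asks for indirect effects through the four mediators and does not require a serial chain. Model 1 uses endline mediators measured in both arms, is fully identified, and delivers that estimand. The text of Section 27a describes one structural model; the serial version appears only in the table shell. Section 14 classes analyses needing midline data as secondary. All of this stands and limits the damage to Model 2. It does not make Model 2 estimable, and Model 1 contains no caregiver-to-parenting paths.

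The mediation figure is not shown and may fix time points, but a diagram cannot supply data that were not collected. That a substitute would be picked after unmasking is a risk, not a certainty.

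A fair point also concerns the remedy. If the caregiver measures and parenting are both taken at endline, the data cannot tell a serial order from correlated parallel mediators, so the chain is then tested only by assumption. This stands and should be said openly in the SAP.

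**Conclusion.** The point holds. With 0% of waitlist midline values observed, the following are not identified in Model 2:

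- a1, a2 and a3, three of the four a-paths
- a4 and c', because both are conditional on the midline mediators
- the serial effects a1 × d1 × b4, a2 × d2 × b4 and a3 × d3 × b4
- the indirect effects a1 × b1, a2 × b2 and a3 × b3
- the total indirect effect, the direct effect and the proportion mediated

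The total effect of BeThere on child wellbeing and its marginal effect on endline parenting remain estimable. Paths d1 to d3 and b1 to b4 are identified under the linear model, but d1 to d3 and b1 to b3 rest on the BeThere arm. The conclusion depends only on the plan's own statements about who was assessed at midline and on reading a1 to a3 as contrasts between arms. It does not depend on the assumed 478 per arm. The primary effectiveness analysis and Model 1 are not affected.

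**What to change.** Re-specify Model 2 in Section 27a and Appendix 1, item 4, on time points measured in both arms: endline caregiver wellbeing, distress and stress, then endline parenting, then follow-up child wellbeing. State the child-wellbeing time point, which the shell leaves open, and state that the order between the caregiver measures and parenting is assumed, not observed. With the first-stage mediators observed in both arms, all 25 parameters are identified.

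Use the midline data only in a BeThere-arm analysis (midline caregiver measures to endline parenting, adjusted for baseline), labelled associational and not as a treatment effect.

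Two alternatives are defensible. One moves parenting to follow-up, which keeps the caregiver-to-parenting order but makes parenting and follow-up child wellbeing concurrent. The other drops Model 2 and relies on Model 1. Whichever is chosen should be fixed in a dated SAP revision before allocation is revealed.

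The cost is wording and one table-shell edit, with no new data. The price of the main option is that the caregiver-to-parenting link becomes concurrent.
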